15.8. Appendix 8: Values of Potential Clinical Importance

ECG values of potential clinical importance are defined as QTc > 500 msec or increase from baseline in QTc \geq 60 msec.

15.9. Appendix 9: Snapshot Algorithm Details

| Detailed Algorithm Steps |
|--|
| 
 Consider an analysis visit window for Week X as defined in Table 10 and Table 13. The HIV-1 RNA threshold of 50, 200 c/mL will be analysed, respectively, in this study The COVID-19 pandemic presents significant logistical challenges for many clinical sites around the world, with variable restrictions being placed on site resources and operations, and on an individual participants ability to attend clinic visits. The snapshot algorithm is modified to allow for the presentation of full scope of COVID-19 relatedness. The analysis window 'Week 48' and HIV-1 RNA threshold of '50 c/mL' are used for the purpose of illustration. A participant's Snapshot response and reason at Week 48 are categorized as below. 
 HIV-1 RNA < 50 c/mL HIV-1 RNA \geq 50 c/mL 
 Data in window not below 50 
 Non-COVID-19 related 
 Discontinued for lack of efficacy Discontinued for other reason while not below 50 Change in background therapy* COVID-19 related 
 Discontinued for lack of efficacy Discontinued for other reason while not below 50 Change in background therapy* No Virologic Data at Week 48 Window 
 Non-COVID-19 related 
 Discontinued study due to AE or death Discontinued study for other reasons On study but missing data in window COVID-19 related 
 Discontinued study due to AE or death Discontinued study for other reasons On study but missing data in window 
* Note: since permanent change in ART are not permitted in this protocol, all such participants who permanently change ART will be considered 'HIV-1 RNA \geq 50 c/mL' if the permanent change in ART is made prior to an analysis timepoint. Participants with protocol permitted temporary oral bridging treatment (CAB+RPV or SOC, the SOC oral bridging medication is permitted during COVID-19 pandemic due to the unavailability of the CAB/RPV IM injections and oral CAB+RPV) or a temporary change in ART by mistake prior to an analysis timepoint (e.g. participant took the ART different from study treatment during oral lead-in by mistake for a short period and then went back to the study treatment) will not be considered 'HIV-1 RNA \geq 50 c/mL' due to 'change in ART'.
 |

- The steps in determining response and reasons are indicated in the table below, in the order stated.
- Background therapy is not given to participants while on study. The “change in background therapy” in detailed steps below refers to the “change in ART” in this study.

| Detailed steps Please note that the following scenarios will NOT be penalized Per Snapshot algorithm (i.e. please exclude these scenarios from Condition 1-4). | | |
|--|---------------------|---|
| Condition ('Week 48' indicates Week 48 window) | Response | Reasons |
| 1. If non-permitted change in background therapy prior to Week 48 | | |
| 1.1. If the change in background therapy is not due to COVID-19 | HIV-1 RNA \geq 50 | Change in background therapy (non-COVID-19 related) |
| 1.2. If the change in background therapy is due to COVID-19 | HIV-1 RNA \geq 50 | Change in background therapy (COVID-19 related) |
| 2. If permitted change ^[a] in background therapy prior to Week 48 AND the latest on-treatment VL prior to/on the date of change is \geq 50 c/mL (NA to this study) | | |
| 2.1 If the change in background therapy is not due to COVID-19 | HIV-1 RNA \geq 50 | Change in background therapy (Non-COVID-19 related) |
| 2.2 If the change in background therapy is due to COVID-19 | HIV-1 RNA \geq 50 | Change in background therapy (COVID-19 related) |
| 3. If non-permitted change in background therapy during Week 48 | | |
| • Last on-treatment VL during Week 48 prior to/on the date of change \geq 50 c/mL | HIV-1 RNA \geq 50 | Data in window not below 50 |
| • Last on-treatment VL during Week 48 prior to/on the date of change $<$ 50 c/mL | HIV-1 RNA $<$ 50 | |
| • No VL during Week 48 prior to/on the date of change and the change in background therapy is not due to COVID-19 | HIV-1 RNA \geq 50 | Change in background therapy (Non-COVID-19 related) |

| | | |
|---|---------------------|---|
| 
 No VL during Week 48 prior to/on the date of change and the change in background therapy is due to COVID-19 | HIV-1 RNA \geq 50 | Change in background therapy (COVID-19 related) |
| 4. If permitted change ^[a] in background therapy during Week 48 AND the last on-treatment VL prior to/on the date of change is \geq 50 c/mL (NA to this study) | | |
| 4.1 This last on-treatment VL occurs prior to Week 48 | | |
| 4.1.1 The change in background therapy is not due to COVID-19 | HIV-1 RNA \geq 50 | Change in background therapy (Non-COVID-19 related) |
| 4.1.2 The change in background therapy is due to COVID-19 | HIV-1 RNA \geq 50 | Change in background therapy (COVID-19 related) |
| 4.2 This last on-treatment VL occurs during Week 48 but prior to/on the date of change | HIV-1 RNA \geq 50 | Data in window not below 50 |
| 5. If none of the above conditions met | | |
| 5.1 On-treatment VL available during Week 48 | | |
| • Last on-treatment VL during Week 48 \geq 50 c/mL | HIV-1 RNA \geq 50 | Data in window not below 50 |
| • Last on-treatment VL during Week 48 $<$ 50 c/mL | HIV-1 RNA $<$ 50 | |
| 5.2 No on-treatment VL during Week 48 | | |
| 5.2.1 If participants are still on study, i.e. a participant has not permanently discontinued the study treatment yet, or if a participant permanently discontinued the study treatment and the upper bound of analysis snapshot window is prior to the following date: Q8W arm: Min[max(Date of last injection + 63, Date of Last Dose of Oral Study Treatment (CAB+RPV, SOC Bridging + 1), Withdrawal Date, LTFU ART Start Date] Q4W arm: Min[max(Date of last injection + 35, Date of Last Dose of Oral Study Treatment (CAB+RPV, SOC Bridging) + 1), Withdrawal Date, LTFU ART Start Date] , where 'Withdrawal Date' refers to the date the participant failed to complete or completed per study conclusion form. | | |

| | | |
|---|-------------------------------------|--|
| 5.2.1.1 If no on-treatment VL during Week 48 is not due to COVID-19 | No virologic data at Week 48 Window | On study but missing data in window (Non-COVID-19 related) |
| 5.2.1.2 If no on-treatment VL during Week 48 is due to COVID-19 | No virologic data at Week 48 Window | On study but missing data in window (COVID-19 related) |
| 5.2.2 If participants withdraw ^[b] before/during Week 48 due to | | |
| 5.2.2.1 Non-COVID-19 related safety reasons (e.g. AE/death, liver chemistry stopping criteria, renal toxicity withdrawal criteria, QTc withdrawal criteria etc, as recorded in eCRF Conclusion form) | No virologic data at Week 48 Window | Disc due to AE/death (Non-COVID-19 related) |
| 5.2.2.2 COVID-19 related safety reasons (e.g. AE/death, liver chemistry stopping criteria, renal toxicity withdrawal criteria, QTc withdrawal criteria etc, as recorded in eCRF Conclusion form) | No virologic data at Week 48 Window | Disc due to AE/death (COVID-19 related) |
| 5.2.2.3 Non-safety and Non-COVID-19 related reasons (e.g. Lack of efficacy, protocol deviation, withdrew consent, loss to follow-up, study closed/terminated, investigator discretion etc, as recorded in eCRF Conclusion Form) | | |
| • Last on-treatment VL <50 c/mL OR no on-treatment VL available during study | No virologic Data at Week 48 Window | Disc for other reasons (Non-COVID-19 related) |
| • Last on-treatment VL ≥ 50 c/mL AND withdrawal due to Lack of efficacy | HIV-1 RNA ≥ 50 | Disc. for lack of efficacy (Non-COVID-19 related) |
| • Last on-treatment VL ≥ 50 c/mL AND withdrawal due to all other non-safety related reasons | HIV-1 RNA ≥ 50 | Disc. for other reason while not below 50 (Non-COVID-19 related) |
| 5.2.2.4 Non-safety and COVID-19 related reasons (e.g. protocol deviation, withdrew consent, loss to follow-up, study closed/terminated, investigator discretion etc, as recorded in eCRF Conclusion Form) | | |
| • Last on-treatment VL <50 c/mL OR no on-treatment VL available during study | No virologic Data at Week 48 Window | Disc for other reasons (COVID-19 related) |

| | | |
|--|---------------------|--|
| 
 Last on-treatment VL \geq 50 c/mL AND withdrawal due to Lack of efficacy | HIV-1 RNA \geq 50 | Disc. for lack of efficacy (COVID-19 related) |
| 
 Last on-treatment VL \geq 50 c/mL AND withdrawal due to all other non-safety related reasons | HIV-1 RNA \geq 50 | Disc. for other reason while not below 50 (COVID-19 related) |
| 
a. Excluding permitted change in background therapy where change or decision to change is made prior to/on the first on-treatment viral result
 
b. Including participants who either prematurely withdraw or complete the study per study conclusion form. In this study, participants who completed the Maintenance phase and decided not to enter the Extension phase without the reason beyond the completion of the study commitment are considered completers per study conclusion form.
 | | |

Examples from FDA guidance

Data in Window

Virologic outcome should be determined by the last available measurement while the patient is on treatment and continued on trial within the time window:

- HIV-1 RNA = 580 c/mL at Day 336, HIV-1 RNA below 50 c/mL on Day 350. This should be categorized as HIV-1 RNA below 50 c/mL.

No Data in Window

Discontinued study due to Adverse Event or Death:

- Any patient who discontinues because of an AE or death before the window should be classified as *Discontinued due to AE or Death* (as appropriate), regardless of the HIV-1 RNA result, even if the HIV-1 RNA is below 50 c/mL at the time of discontinuation.
- However, if a patient has an HIV-1 RNA value in the time window and also discontinues in the time window, the viral load data should be used to classify the patient's response. This is the Virology First hierarchy:
 - HIV-1 RNA below 50 c/mL at Day 336 and discontinues because of AE or even dies on Day 360 — this person is categorized as having HIV-1 RNA below 50 c/mL.
 - HIV-1 RNA is 552 c/mL on Day 336 and the patient discontinues on Day 360, the patient is categorized as having HIV-1 RNA \geq 50 c/mL.

Discontinued for Other Reasons:

- Only patients who have achieved virologic suppression can be counted as *Discontinued for Other Reasons*.
- If a patient discontinues the study before the time window because of *lack of efficacy* then the patient should be included in the HIV-1 RNA \geq 50 row and not in the Discontinued for Other Reasons row.
- If a patient discontinues because *participant withdrew consent* and his or her HIV-1 RNA result at the time of discontinuation was equal to or above 50 c/mL, then he or she should be categorized as HIV-1 RNA \geq 50 and NOT as Discontinued for Other Reasons.

- If a patient discontinued because of *Lost to Follow-Up* and the last HIV-1 RNA result was 49 c/mL, then the patient can be categorized as Discontinued for Other Reasons.
- If patients changed background treatment — *not permitted by protocol*— they should be considered an efficacy failure and captured in the HIV-1 RNA ≥ 50 c/mL row.

On study but missing data in window:

- If there are no data during Days 294 to 377, but there is an HIV-1 RNA below 50 c/mL on Day 380, this patient should be considered *On Study but Missing Data in Window*.
- If there are no data during Days 294 to 377, but there is an HIV-1 RNA equal to or above 50 c/mL on Day 280, this patient also should be classified as *On Study but Missing Data in Window*.

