5.2. Baseline Definitions

For all endpoints (except as noted in baseline definitions) the baseline value will be the latest pre-treatment (see [Table 8](#)) assessment with a non-missing value, including those from unscheduled visits. ‘Pre-treatment’ in main study refers to prior to the study treatment (i.e. CAB and/or RPV) in this study, and ‘pre-treatment’ in sub-study refers to prior to the first CAB and/or RPV thigh injection.

Electrocardiograms (ECGs) are to be performed in triplicate on main study Day 1 visit. The baseline value for an ECG parameter will be the mean of the last pre-treatment set of assessments from the same date, so long as at least one of the triplicate assessments is available.

Unless otherwise stated, if baseline data is missing no derivation will be performed and baseline will be set to missing.

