| Min(7*w + 2, first thigh injection date+1) ≤ Study Day ≤ 7*(w+6) | Min (7*w + 2, first thigh injection date+1) ≤ Study Day ≤ 7*(w+10) | Sub-study Week 4 |
| 7*(w+6) + 1 ≤ Study Day ≤ 7*(w+10) | 7*(w+6) + 1 ≤ Study Day ≤ 7*(w+14) | Sub-study Week 8 |
| 7*(w+10) + 1 ≤ Study Day ≤ 7*(w+14) | 7*(w+10) + 1 ≤ Study Day ≤ 7*(w+16) | Sub-study Week 12 |
| 7*(w+10) + 1 ≤ Study Day ≤ 7*(w+22) | 7*(w+10) + 1 ≤ Study Day ≤ 7*(w+22) | Sub-study Week 16 |
| NOTES: 
 The “w” in the target study day calculation refers to the corresponding week number in Extension for the planned Sub-study Day 1 visit. For example, if a participant’s last planned Extension phase visit before entering | | |

| |
|---|
| the Sub-study is Week 192, the "w" would be 200 if the participant is on Q4W arm and would be 208 if the participant is on Q8W arm. |
| • For post-baseline visits (i.e. Week 4 and afterwards), apply Snapshot analysis windows only to viral load data that is on-treatment (per Table 20) within the Thigh Injection Phase (per Table 18). |
| • An on-treatment viral load assessment may be assigned to more than one snapshot analysis window, e.g. on-treatment assessment taken on $7^*(w+14)$ will be in both Sub-study Week 12 and Sub-study Week 16 visits. |
| • ± 6 Week window is always used at the key analysis timepoint, Sub-study Week 16 visit. |
| [a] The values considered for deriving Sub-study Baseline value include both Extension phase and sub-study data. |

Table 14 Assessment Windows for Summaries of Long-Term Follow Up Phase Data for Participants Who Received At Least One Injection of CAB+RPV and Permanently Discontinued Study Treatment

| Analysis Window | Analysis Timepoint | Target Study Day of Window |
|---|-------------------------------------|----------------------------|
| $1 \leq \text{LTFU Study Day} \leq 63$ | LTFU Month 1/WD ^[a] | 30 |
| $64 \leq \text{LTFU Study Day} \leq 135$ | LTFU Month 3 | 90 |
| $136 \leq \text{LTFU Study Day} \leq 225$ | LTFU Month 6 | 180 |
| $226 \leq \text{LTFU Study Day} \leq 315$ | LTFU Month 9 | 270 |
| $316 \leq \text{LTFU Study Day} \leq 405$ | LTFU Month 12 | 360 |
| $(30^*m - 44) \leq \text{LTFU Study Day} \leq (30^*m + 45)$ | LTFU Month m m = 15, 18, 21, ... | 30^*m |

NOTES:

- An assessment may be assigned to both LTFU and maintenance/extension phases.

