| Sub-study Screening | 
For participants entering the sub-study and not receiving any thigh injection:
 
If participants continued into LTFU Phase after the sub-study, then Date of First sub-study record \leq Date $<$ LTFU ART Start Date^[b]
 
If participants transitioned to marketed product/alternative HAART and did not withdraw study due to safety related reason, then Date of First sub-study record \leq Date $<$ Date of end of study +35 days (Q4W) or + 63 days (Q8W)
 
If participants continued into Extension Phase after the sub-study, then Date of First sub-study record \leq Date \leq End of Sub-study Date^[c]
 
For participants entering the sub-study and receiving thigh injection(s):
 
Date of First sub-study record \leq Date \leq Date of First Thigh Injection^[d]
 |
| Thigh Injection | 
For participants continuing into Return to Gluteal Injection Phase:
 
Date of First Thigh Injection^[d] $<$ Date \leq Date of Nominal Sub-study Week 16 Visit^[e]
 
For participants not continuing into Return to Gluteal Injection Phase:
 
If participants continued into LTFU Phase after the sub-study, then Date of First Thigh Injection^[d] $<$ Date \leq LTFU ART Start Date^[b]
 
If participants continued into Extension Phase after the sub-study, then Date of First Thigh Injection^[d] $<$ Date \leq End of Sub-study Date^[c]
 
If participants transitioned to marketed product/alternative HAART and did not withdraw study due to safety related reason, then Date of First Thigh Injection \leq Date \leq Date of end of study +35 days (Q4W) or + 63 days (Q8W)
 |
| Return to Gluteal Injection | 
For participants continuing into Return to Extension Phase after the sub-study:
 
Date of Nominal Sub-study Week 16 Visit^[e] $<$ Date \leq End of Sub-study Date^[c]
 
For participants continuing into LTFU Phase after the sub-study:
 
Date of Nominal Sub-study Week 16 Visit^[e] $<$ Date \leq LTFU ART Start Date^[b]
 
For participants transitioned to marketed product/alternative HAART and did not withdraw study due to safety related reason:
 
Date of Nominal Sub-study Week 16 Visit^[c] $<$ Date \leq Date of end of study +35 days (Q4W) or + 63 days (Q8W)
 |

- Date = start or assessment date
- [a] If the collected time of the assessment is available, the assessment taken on the same day as nominal Week 100 visit date but after the Week 100 injection will be assigned to Extension Phase.

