15.6. Appendix 6: Derived and Transformed Data

15.6.1. General

| |
|---|
| Multiple Measurements at One Time Point |
| 
 If after window assignment there are multiple valid assessments of a parameter within the same window, refer to Section 15.3.5.1 for determination of the value to be used for summary statistics of observed values. Assessments not chosen for use in summary statistics will still appear in the associated listings. Assessments not chosen for use in summary statistics by this algorithm will still appear in the associated listings. Also, all applicable valid assessments, irrespective of proximity to the target study day, will be used when categorizing values across visits, such as 'maximum grade' or 'at any time', and for any algorithm that has specific rules for which observation to use (e.g. snapshot algorithm, LOCF or CVF identification). |
| Nominal Week 100 Visit Date |
| 
 For participants who received Week 100 injection, nominal Week 100 visit date is defined by the Week 100 injection date. Otherwise, nominal Week 100 visit date is defined by the date of latest Week 100 assessment. For participants who continued into Extension Phase however missed Week 100 visit, nominal Week 100 visit date is defined by the end of Maintenance Phase date (i.e. date for the Maintenance Phase conclusion record in the SDTM DS domain) for the analysis purpose. |
| Nominal Sub-study Week 16 Visit Date |
| 
 For participants who received Sub-study Week 16 injection, nominal Sub-study Week 16 visit date is defined by the Sub-study Week 16 injection date. Otherwise, nominal Sub-study Week 16 visit date is defined by the date of latest Sub-study Week 16 assessment. For participants who continued into Return to Gluteal Injection Phase however missed Sub-study Week 16 visit, nominal Sub-study Week 16 visit date is defined by the end of Thigh Injection Phase date (i.e. date for the Thigh Injection Phase conclusion record in the SDTM DS domain) for the analysis purpose. |
| End of Sub-study Date |
| 
 For sub-study screen failures, the end of sub-study date is defined by the date they failed to meet the inclusion/exclusion criteria in the sub-study. For other sub-study participants, the end of sub-study date is defined by the date of completion or withdrawal available in the sub-study conclusion eCRF form. |

Study Day

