15.15.7.1. Study Population Tables

| Study Population Tables | | | | | |
|----------------------------|--------------------|------------------------|--|--|-------------|
| No. | Population | IDSL / Example Shell | Title | Programming Notes | Deliverable |
| Subject Disposition | | | | | |
| 1.1 | Sub-study ITT-E | 207966/primary_34/T1.1 | Summary of Number of Sub-study Subjects Enrolled by Country and Site ID | | Sub-study |
| 1.2 | Sub-study Screened | 207966/primary_15/T1.2 | Summary of Screening Status and Reasons for Sub-study Screening Failures | | Sub-study |
| 1.3 | Sub-study ITT-E | 207966/primary_34/T1.2 | Summary of Subject Accountability: Sub-study Conclusion Record | Remove the first footnote. Re-number the footnotes and the corresponding numbers in the display. | Sub-study |
| 1.4 | Sub-study ITT-E | 207966/primary_34/T1.3 | Summary of Subject Accountability: Thigh Injection Phase Conclusion Record | | Sub-study |
| 1.5 | Sub-study ITT-E | 207966/primary_34/T1.3 | Summary of Subject Accountability: Return to Gluteal Injection Phase Conclusion Record | | Sub-study |
| 1.6 | Sub-study ITT-E | 207966/primary_34/T1.6 | Summary of Subject Disposition at Each Study Phase | Present following phases in order: Thigh Injection Phase, Extension Phase (after withdrawal from the Thigh Injection phase), Long-term Follow-up Phase (after withdrawal from the Thigh Injection phase), Return to Gluteal Injection Phase, | Sub-study |

| Study Population Tables | | | | | |
|--|--------------------|-------------------------|--|---|-------------|
| No. | Population | IDSL / Example Shell | Title | Programming Notes | Deliverable |
| | | | | Extension Phase (after withdrawal from the Return to Gluteal Injection phase or sub-study completion), Long-term Follow-up Phase (after withdrawal from the Return to Gluteal Injection phase or sub-study completion). | |
| 1.7 | Sub-study ITT-E | 207966/primary_34/T1.9 | Summary of Study Drug Discontinuation | | Sub-study |
| 1.8 | Sub-study Screened | 207966/primary_34/T1.10 | Summary of Study Populations | Only include analysis populations used in the sub-study analysis. | Sub-study |
| 1.9 | Sub-study ITT-E | 207966/primary_34/T1.11 | Summary of Important Protocol Deviations in Sub-study | | Sub-study |
| 1.10 | Sub-study ITT-E | 207966/primary_34/T1.11 | Summary of Important Protocol Deviations (Thigh Injection Phase) | | Sub-study |

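### Sub-study Snapshot: a participant who leaves thigh injections viraemic before Day 71 and returns to gluteal dosing is counted at Week 16 as on study with missing data, not as HIV-1 RNA ≥50

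*SAP*

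**What the plan says.** Appendix 9 (Section 15.9) serves both main study and sub-study: "Consider an analysis visit window for Week X as defined in Table 10 and Table 13". It gives no exception for the sub-study.

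The notes to Table 13 (Section 15.3.2) restrict the eligible data: "apply Snapshot analysis windows only to viral load data that is on-treatment (per Table 20) within the Thigh Injection Phase (per Table 18". For a participant who goes straight from thigh injections back to the Extension Phase, Table 18 (Section 15.4.1) bounds the thigh phase with "If participants continued into Extension Phase after the sub-study, then Date of First Thigh Injection" as the lower limit and the End of Sub-study Date as the upper. Section 15.6.1 says of that end point that "the end of sub-study date is defined by the date of completion or withdrawal available in the sub-study conclusion eCRF form".

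With no qualifying value in the window, step 5.2.1 comes first: "If participants are still on study, i.e. a participant has not permanently discontinued the study treatment yet". The Withdrawal Date used in that step "refers to the date the participant failed to complete or completed per study conclusion form". The branches that return ≥50 from the last on-treatment viral load (5.2.2.3 and 5.2.2.4) apply only after withdrawal.

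The plan expects this route. Its disposition table for the sub-study (Section 15.15.7.1, Table 1.6) has a row "Extension Phase (after withdrawal from the Thigh Injection phase").

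**The concern.** In the sub-study the thing under test is the thigh route. Returning to gluteal dosing ends exposure to that route but not to CAB+RPV. Step 5.2.1 recognises only the end of CAB+RPV, and it reads the date from the overall study form, not from the record that closes the thigh phase. A viraemic participant who leaves the thigh phase early therefore never reaches step 5.2.2, where the last thigh-phase viral load would be looked at.

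That conflicts with Section 15.6.3, which places non-AE withdrawals who were not suppressed in the ≥50 category. At stake is the ≥50 count at Sub-study Week 16, the timepoint the SAP names in the endpoint and treats as key.

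**Working it through.** The plan states no figure to reproduce. The check applies the rules in order to defined cases.

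**Window.** Table 13 gives Week 16 as 7(w+10)+1 to 7(w+22). Counted from planned sub-study Day 1 (subtract 7w), that is Day 71 to Day 154. The target is 7×16+1 = Day 113, and 113−42 = 71 and 113+41 = 154. Main-study Week 48 follows the same convention: 337−42 = 295 and 337+41 = 378.

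**Meaning of study treatment.** Section 5.2 glosses the main-study term as "prior to the study treatment (i.e. CAB and/or RPV) in this study". Table 20 reuses the Extension Phase on-treatment rules for the sub-study phases and has no thigh-specific stop. Steps 1 to 4 of Appendix 9 concern a change in ART, so a change of injection site does not trigger them.

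**Cases.** The assumptions are: last thigh-phase value 120 c/mL; non-AE reason; End of Sub-study Date equal to the day of leaving; a later gluteal (Extension Phase) value of 30 c/mL on Day 113.

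| Participant | Day of leaving | Week 16 as written | Same person, had all CAB+RPV stopped |
|---|---|---|---|
| Q8W, leaves at Week 8 | 57 | No virologic data, on study but missing | ≥50 |
| Q4W, leaves at Week 4 | 29 | No virologic data, on study but missing | ≥50 |
| Q4W, leaves at Week 8 | 57 | No virologic data, on study but missing | ≥50 |
| Q4W, leaves at Week 12 | 85 | ≥50 (value already in window) | ≥50 |

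In the first three rows the 120 c/mL value falls before Day 71, and the Day 113 value lies outside the thigh phase. Nothing qualifies under step 5.1, and step 5.2.1 then catches the participant. The last row shows the limit: a viraemic thigh-phase value from Day 71 on is still counted.

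**Size.** The SAP plans about 82 participants, 41 per arm. Each affected participant is 1/41 = 2.4 points in one arm, or 1/82 = 1.2 points overall. Exact (Clopper-Pearson) 95% limits at n = 41, where the upper limit for zero events is 1 − 0.025^(1/41) = 8.6%:

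- 0/41 = 0% (0 to 8.6%)
- 1/41 = 2.4% (0.1 to 12.9%)
- 2/41 = 4.9% (0.6 to 16.5%)

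The counts of 1 and 2 are illustrations. The SAP gives no basis for an expected number.

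**The case against.** **The terms may be meant to adapt.** Section 5.2 goes on to tie pre-treatment in the sub-study to the first thigh injection, and Appendix 9 says Week 48 is used only for illustration. But the Section 5.2 sentence redefines pre-treatment, not study treatment or its discontinuation, and step 5.2.1 names the study conclusion form. The literal rule stands.

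**Pre-window viraemia is sometimes rightly classed as missing.** One of the guidance examples in Appendix 9 has a value ≥50 on Day 280, no data in the Week 48 window, and the outcome on study but missing. That participant is still on the treatment under test; the sub-study leaver is not.

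**Reach is small.** This stands. The participant must leave, and the phase must close, before Day 71; if the sub-study conclusion date is later, a viral load drawn in between counts. Two consecutive values ≥200 c/mL are confirmed virologic failure, and if CAB+RPV is then stopped, step 5.2.2 applies. The gap is mainly viraemia that is not confirmed failure.

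**Stronger readings that the SAP does not support.** A reader might infer that the rule flatters the suppression result. It does not: a participant with no virologic data stays in the Sub-study ITT-E denominator and is not counted as <50, so the <50 proportion is the same under either rule. A reader might also infer that viraemia or tolerability exits are hidden. Viraemia at Weeks 4 and 8 still appears in the by-visit Snapshot (sub-study Table 2.3) and in Listings 32 and 33. AE leavers are no virologic data under both rules, and their exits are reported in Table 1.4, Tables 3.17 and 3.18, and Listing 23.

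**Conclusion.** The point holds in a narrow form. A non-AE leaver whose last thigh-phase HIV-1 RNA is ≥50, with no thigh-phase viral load from Day 71 on and a return to gluteal CAB+RPV in the Extension Phase, goes into the wrong Week 16 category when Appendix 9 is followed as written. The error runs one way: the ≥50 proportion can only be too low, by 2.4 points per participant in an arm of 41. For AE leavers only the sub-reason is wrong, reading on study but missing instead of discontinued due to AE.

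This rests on the literal wording of step 5.2.1 and on the phase limits of Table 18. How many participants it touches cannot be known from the SAP. It deserves correction because the plan foresees the route and the result departs from the plan's own principle.

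**What to change.** Add one sentence to Appendix 9: for Table 13 windows, permanent discontinuation of study treatment and withdrawal both mean withdrawal from the Thigh Injection Phase, with date and reason taken from that phase's conclusion record. Early leavers with no qualifying viral load in the window then go to step 5.2.2 and are classified by their last Thigh Injection Phase viral load and their stop reason.

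The record already exists: sub-study Table 1.4 summarises it, and Section 15.6.1 uses its date. Appendix 10 already works from a phase-specific conclusion form for the Maintenance Phase. No new data are needed. The cost is a small change to the sub-study Snapshot program and a ≥50 proportion that may come out slightly less favourable.
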